6.4. Covariates and Subgroups

As a protocol defined exploratory analysis, HAI antibody response following the second vaccination will be summarized stratified by the following covariates: age (categorical: 19-34, 35-50), sex (male, female), body mass index (<30, ≥30), and prior receipt of seasonal influenza vaccine(s). Prior receipt of influenza vaccines, including any reported prior receipt of A/H5 vaccinations, or reported seasonal vaccination receipt will also be included as covariates. Summaries of prior seasonal vaccination will include breakdowns of receipt of the two seasonal vaccinations prior to study initiation (did not receive 2016-2017 or 2018-2019; received 2016-2017 and/or 2018-2019) as well as independently assessing subject receipt of 2018-2019 seasonal vaccine (did not receive/received) prior to the second dose of study vaccine. These covariates will be considered in statistical modeling as described in Section 8.3. As these analyses are exploratory, the study was not powered for any subgroup analyses.

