6.7. Multicenter Studies

Randomization was stratified by site, but data will be pooled across all clinical sites for all analyses. Center effects are not anticipated because the sites use standardized procedures for vaccination and assessment of solicited and unsolicited AEs, and the study relies on a central laboratory for immunogenicity assessments.

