8.3.1. HAI and Neut Covariate Analysis

As an exploratory analysis, seroconversion and GMT of serum antibody for both HAI and Neut against the homologous 2013 A/H7N9 strain at 21 and 180 days after the second study vaccination will be summarized by study group stratified by age (categorized as those subjects ages 19-34, 35-50 years) (Table 32, Table 33, Table 34, and Table 35), by sex (Table 40, Table 41, Table 42, and Table 43), by BMI (Table 48, Table 49, Table 50, and Table 51), and by prior receipt of the 2016-2017 and/or 2017-2018 and /or 2018-2019 seasonal influenza vaccines (Table 56, Table 57, Table 58, and Table 59). These analyses will be repeated for HAI and Neut titer results against the 2017 A/H7N9 strain at 21 and 180 days post receipt of the second study vaccination by age category (Table 36, Table 37, Table 38, and Table 39) by sex (Table 44, Table 45, Table 46, and Table 47), by BMI (Table 52, Table 53, Table 54, and Table 55) by prior receipt of seasonal influenza vaccine (Table 60, Table 61, Table 62, and Table 63).

The stratified summaries will be presented for the PP population. It is anticipated that subjects will have little to no pre-existing antibody at baseline, so seroconversion and titer ≥ 40 endpoints will be similar.

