8.3.2. HAI and Neut Regression Modeling

Regression modeling will be utilized to test for the effect of treatment variables i.e. prime boost combination (*PrimeBoost*), Boost dose (*BoostDose*), and interval between vaccinations (*Interval*), on immune response. Logistic regression will be fit for the seroconversion outcome. If the available titer data meet the required assumptions of normality after log transformation, multiple linear regression will be fit to log-transformed titers. Separate models will be fit for each assay (HAI, Neut), each strain (2013 A/H7N9, 2017 A/H7N9) and each time point (Day 22 post vaccination 1, Day 22 post vaccination 2, Day 181 post vaccination 2). All models will be fit with a similar structure for *PrimeBoost*, *BoostDose*, *Interval*, and covariates, for the PP population. The treatment variables will be defined as *PrimeBoost* (homologous, heterologous), *BoostDose* (3.75 mcg+AS03, 15 mcg), and *Interval* (21 days, 120 days). All models will be fit with and without adjustment for the following covariates (*Z*): age in years, sex (female, male), BMI (<30, ≥ 30), and prior receipt of seasonal influenza vaccine in the current season (did not receive 2018-2019 seasonal influenza vaccine, received 2018-2019 seasonal influenza vaccine) (did not receive 2016-2017 or 2017-2018 seasonal influenza vaccines, received 2016-2017 and/or 2017-2018 seasonal influenza vaccine). The models as shown below assume a linear relationship between age in years and both probability of seroconversion and GMT. The validity of this assumption will be assessed prior to analysis and, if the relationship between age and response is found to be non-linear, adjustments will be made to model parameters to satisfy regression assumptions. Modeling assumptions will be checked using standard diagnostic methods (e.g., using the INFLUENCE option in PROC LOGISTIC or PROC GLM). Parameter estimates and odds ratio estimates for the logistic models will be presented for the 2013 and 2017 A/H7N9 strains without covariate adjustment in Table 64, Table 65, Table 66, Table 67, and with covariate adjustment in Table 68, Table 69, Table 70, Table 71. Parameter estimates for the multiple linear regression models will be presented for the 2013 and 2017 A/H7N9s strain without covariate adjustment in Table 72, Table 73, Table 74, Table 75, and with covariate adjustment in Table 76, Table 77, Table 78, Table 79.

Model 1A: Logistic Regression (without covariate adjustment):

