$$\begin{aligned} \text{logit}[P(\text{seroconversion})] \\ = \beta_0 + \beta_1 \times \text{PrimeBoost} + \beta_2 \times \text{BoostDose} + \beta_3 \times \text{Interval} \\ + \beta_4 \times (\text{PrimeBoost} * \text{BoostDose}) + \beta_5 \times (\text{PrimeBoost} * \text{Interval}) + \varepsilon \end{aligned}$$

Model 1B: Logistic Regression (with covariate adjustment):

$$\begin{aligned} \text{logit}[P(\text{seroconversion})] &= \beta_0 + \beta_1 \times \text{PrimeBoost} + \beta_2 \times \text{BoostDose} + \beta_3 \times \text{Interval} \\ &+ \beta_4 \times (\text{PrimeBoost} * \text{BoostDose}) + \beta_5 \times (\text{PrimeBoost} * \text{Interval}) + \beta_6 \times Z + \varepsilon \end{aligned}$$

Model 2A: Multiple Linear Regression (without covariate adjustment):

$$\begin{aligned} \log(\text{titer}) &= \beta_0 + \beta_1 \times \text{PrimeBoost} + \beta_2 \times \text{BoostDose} + \beta_3 \times \text{Interval} \\ &+ \beta_4 \times (\text{PrimeBoost} * \text{BoostDose}) + \beta_5 \times (\text{PrimeBoost} * \text{Interval}) + \varepsilon \end{aligned}$$

Model 2B: Multiple Linear Regression (with covariate adjustment):

$$\begin{aligned} \log(\text{titer}) &= \beta_0 + \beta_1 \times \text{PrimeBoost} + \beta_2 \times \text{BoostDose} + \beta_3 \times \text{Interval} + \beta_4 \times (\text{PrimeBoost} * \text{BoostDose}) \\ &+ \beta_5 \times (\text{PrimeBoost} * \text{Interval}) + \beta_6 \times Z + \varepsilon \end{aligned}$$

Where Z is the matrix of covariates age, sex, BMI, and prior receipt of seasonal influenza vaccine as defined in Section 6.4. Subjects missing data for one or more covariates will be excluded from Models 1B and 2B.

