9.1. Demographic and Other Baseline Characteristics

Summaries of age, sex, ethnicity, race, BMI, and prior receipt of seasonal influenza vaccine will be presented by site ([Table 19](#), [Table 20](#)) and by study group ([Table 21](#), [Table 22](#)). Age will be summarized as a continuous variable. Ethnicity is categorized as Hispanic or Latino, or not Hispanic and not Latino. In accordance with NIH reporting policy, subjects may self-designate as belonging to more than one race or may refuse to identify a race, the latter reflected in the electronic case report form (eCRF) as “No” to each racial option. BMI will be summarized as a continuous as well as categorical variable, categorized as (<30, ≥30). Self-reported history of prior receipt of influenza vaccines will be broken down by the following categories: receipt of seasonal vaccines for prior seasons (2016-2017, 2017-2018), receipt of seasonal vaccine for the current season (2018-2019; considered up to receipt of study dose 2), and receipt of any A/H5 vaccines prior to enrollment. Demographic information for individual subjects will be provided in [Listing 6](#). Subjects’ prior influenza vaccination history (seasonal and non-seasonal) will be provided in [Listing 8](#).

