- Table 52:** Summary of Hemagglutination Inhibition Antibody Against A/Hong Kong/125/2017 (A/H7N9) by Study Group and BMI at 21 Days Post Second Vaccination, Per Protocol Population
- Table 53:** Summary of Hemagglutination Inhibition Antibody Against A/Hong Kong/125/2017 (A/H7N9) by Study Group and BMI at 180 Days Post Second Vaccination, Per Protocol Population
- Table 54:** Summary of Neutralizing Antibody Against A/Hong Kong/125/2017 (A/H7N9) by Study Group and BMI at 21 Days Post Second Vaccination, Per Protocol Population
- Table 55:** Summary of Neutralizing Antibody Against A/Hong Kong/125/2017 (A/H7N9) by Study Group and BMI at 180 Days Second Vaccination, Per Protocol Population

Table 56: Summary of Hemagglutination Inhibition Antibody Against A/Shanghai/2/2013 (A/H7N9) by Study Group and Seasonal Influenza Vaccination Status at 21 Days Post Second Vaccination, Per Protocol Population

| Receipt of 2018-2019 Seasonal Influenza Vaccine | Statistic | Group 1 2013 3.75+AS03/ 2017 3.75+AS03 (D1-D22) (N=X) | Group 2 2013 3.75+AS03/ 2017 3.75+AS03 (D1-D121) (N=X) | Group 3 2013 3.75+AS03/ 2017 15 (D1-D121) (N=X) | Group 4 2017 3.75+AS03/ 2017 3.75+AS03 (D1-D22) (N=X) | Group 5 2017 3.75+AS03/ 2017 3.75+AS03 (D1-D121) (N=X) | Group 6 2017 3.75+AS03/ 2017 15 (D1-D121) (N=X) |
|--|--|---|--|---|---|--|---|
| Did Not Receive Prior 2016-2017 or 2017-2018 Seasonal Influenza Vaccination | | | | | | | |
| Did Not Receive 2018-2019 Seasonal Influenza Vaccine | n | x | x | x | x | x | x |
| | GMT (95% CI) ^a | xxx.x(xxx.x,xxx.x) | xxx.x(xxx.x,xxx.x) | xxx.x(xxx.x,xxx.x) | xxx.x(xxx.x,xxx.x) | xxx.x(xxx.x,xxx.x) | xxx.x(xxx.x,xxx.x) |
| | Titer ≥ 1:40 - %(95% CI) ^b | xx (xx, xx) | xx (xx, xx) | xx (xx, xx) | xx (xx, xx) | xx (xx, xx) | xx (xx, xx) |
| | GMFR (95% CI) ^a | xxx.x(xxx.x,xxx.x) | xxx.x(xxx.x,xxx.x) | xxx.x(xxx.x,xxx.x) | xxx.x(xxx.x,xxx.x) | xxx.x(xxx.x,xxx.x) | xxx.x(xxx.x,xxx.x) |
| | Seroconversion - % (95% CI) ^b | xx (xx, xx) | xx (xx, xx) | xx (xx, xx) | xx (xx, xx) | xx (xx, xx) | xx (xx, xx) |
| Received 2018-2019 Seasonal Influenza Vaccine | n | x | x | x | x | x | x |
| | GMT (95% CI) ^a | xxx.x(xxx.x,xxx.x) | xxx.x(xxx.x,xxx.x) | xxx.x(xxx.x,xxx.x) | xxx.x(xxx.x,xxx.x) | xxx.x(xxx.x,xxx.x) | xxx.x(xxx.x,xxx.x) |
| | Titer ≥ 1:40 - %(95% CI) ^b | xx (xx, xx) | xx (xx, xx) | xx (xx, xx) | xx (xx, xx) | xx (xx, xx) | xx (xx, xx) |

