| | 3.75 mcg + AS03 | xxx.x | xxx.x | x.xxx | xx.x | xx.x-xx.x | xxx.x | xxx.x | x.xxx | xx.x | xx.x-xx.x |
| Interval | 21 days (reference) | - | - | - | - | - | - | - | - | - | - |
| | 120 days | xxx.x | xxx.x | x.xxx | xx.x | xx.x-xx.x | xxx.x | xxx.x | x.xxx | xx.x | xx.x-xx.x |
| Age (years) | N/A | xxx.x | xxx.x | x.xxx | xx.x | xx.x-xx.x | xxx.x | xxx.x | x.xxx | xx.x | xx.x-xx.x |
| Sex | Female (reference) | - | - | - | - | - | - | - | - | - | - |
| | Male | xxx.x | xxx.x | x.xxx | xx.x | xx.x-xx.x | xxx.x | xxx.x | x.xxx | xx.x | xx.x-xx.x |
| BMI | <30 (reference) | - | - | - | - | - | - | - | - | - | - |
| | ≥30 | xxx.x | xxx.x | x.xxx | xx.x | xx.x-xx.x | xxx.x | xxx.x | x.xxx | xx.x | xx.x-xx.x |
| Prior Receipt of Influenza Vaccine (Prior Seasons) | Did Not Receive 2016-2017 or 2017-2018 Seasonal Influenza Vaccination (reference) | - | - | - | - | - | - | - | - | - | - |
| | Received 2016-2017 and/or 2017-2018 Seasonal Influenza Vaccination | xxx.x | xxx.x | x.xxx | xx.x | xx.x-xx.x | xxx.x | xxx.x | x.xxx | xx.x | xx.x-xx.x |

| Model Parameter | Parameter Category | A/Shanghai/2/2013 (A/H7N9) | | | | | A/Hong Kong/125/2017 (A/H7N9) | | | | |
|--|--|----------------------------|-------|---------|------------|-----------|-------------------------------|-------|---------|------------|-----------|
| | | Parameter Estimate | SE | p-value | Odds Ratio | 95%CI | Parameter Estimate | SE | p-value | Odds Ratio | 95%CI |
| Receipt of Influenza Vaccine (Concurrent Season) | Did Not Receive 2018-2019 Seasonal Influenza Vaccine (reference) | - | - | - | - | - | - | - | - | - | - |
| | Received 2018-2019 Seasonal Influenza Vaccine (reference) | xxx.x | xxx.x | x.xxx | xx.x | xx.x-xx.x | xxx.x | xxx.x | x.xxx | xx.x | xx.x-xx.x |
| Prior Receipt of H5 Influenza Vaccine | No Prior H5 Influenza Vaccinations | - | - | - | - | - | - | - | - | - | - |
| | Received Prior H5 Influenza Vaccinations | xxx.x | xxx.x | x.xxx | xx.x | xx.x-xx.x | xxx.x | xxx.x | x.xxx | xx.x | xx.x-xx.x |

Note: Receipt of 2018-2019 vaccine is counted at any timepoint prior to receipt of the second study vaccination.
n= XX (number of subjects with results available at 21 days post second study vaccination in the Per Protocol Population).
XX subjects missing covariate data were excluded from this analysis.
SE = Standard Error.

Tables with similar format:

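### SAP 6.4 defines the prior-season vaccine covariate with the wrong season, under circular cross-references; separately, the linear titer models could cheaply use the randomisation strata, except the vaccine stratum in Model 2B

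*SAP*

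**What the plan says.** **Season definition.** SAP 6.4 gives the breakdown of prior vaccination as "the two seasonal vaccinations prior to study initiation (did not receive 2016-2017 or 2018-2019; received 2016-2017 and/or 2018-2019" and, in the same sentence, lists 2018-2019 receipt again as an independent item. SAP 8.3.2 gives the model covariate as "did not receive 2016-2017 or 2017-2018 seasonal influenza vaccines, received 2016-2017 and/or 2017-2018 seasonal influenza vaccine", with 2018-2019 as its own term. SAP 9.1 uses "receipt of seasonal vaccines for prior seasons (2016-2017, 2017-2018), receipt of seasonal vaccine for the current season" for 2018-2019. The Table 56 shell has a block headed "Did Not Receive Prior 2016-2017 or 2017-2018 Seasonal Influenza Vaccination", crossed with 2018-2019 receipt, and the shells of Tables 68 and 76 use the same pair. Protocol 8.1.1 calls 2018-2019 the current season and 2016-2017 and 2017-2018 the previous two. SAP 8.3.1 has a third wording, "by prior receipt of the 2016-2017 and/or 2017-2018 and /or 2018-2019 seasonal influenza vaccines".

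**Which definition the models use.** SAP 6.4 says its covariates enter modelling as described in Section 8.3. SAP 8.3.2 spells out its list and then adds: "Where Z is the matrix of covariates age, sex, BMI, and prior receipt of seasonal influenza vaccine as defined in Section 6.4".

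**Strata.** Protocol 5.2.1 and SAP 4.4.3 stratify randomisation by site and by prior seasonal vaccine. The protocol defines the latter as receipt in 2017-2018 and/or 2018-2019. SAP 6.7 states: "Randomization was stratified by site, but data will be pooled across all clinical sites for all analyses". Its reason is that no centre effects are expected. Model 2A has treatment terms only. Model 2B adds age, sex, BMI and vaccine history, and its shell also has prior H5 vaccination. Site is in neither. The Table 68 and 76 footnote reads: "Note: Receipt of 2018-2019 vaccine is counted at any timepoint prior to receipt of the second study vaccination".

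**The concern.** A covariate rule in the SAP contradicts the model section and the shells, and the sentence defining the covariate matrix points at the wrong one. Programmed literally, a subject vaccinated only in 2017-2018 is coded as having no prior-season vaccine, and a subject vaccinated only in 2018-2019 is coded as having had it. The outputs exposed are the covariate-adjusted models (Tables 68-71 and 76-79) and, if 6.4 is taken to govern the stratified summaries, Tables 56-63.

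The second matter is an improvement rather than an error. Stratified randomisation balances the arms on the strata, so the treatment estimates already benefit from that balance. A linear model that leaves the strata out still counts their variation as residual error. If the strata predict titer, the reported standard errors are then larger than they need be.

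**Working it through.** **1. Season coding.** Write a vaccination history as (2016-17, 2017-18, 2018-19). Of the eight histories, the two definitions disagree on two:

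| History | SAP 6.4 | SAP 8.3.2 | Randomisation stratum |
|---|---|---|---|
| 0,1,0 | no | yes | yes |
| 0,0,1 | yes | no | yes |

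Under 6.4, with 2018-2019 counted over the same window in both terms, the cell for no prior vaccine but 2018-2019 received is empty by construction. If the pair is cut off at study start, the cell holds only subjects vaccinated between Day 1 and Dose 2.

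Uptake is not in the documents. Assume uptake p in every season (0.3 to 0.5) and a first-order chain with lag-1 correlation r (0 to 0.7), with N = 180:

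- 2017-2018 only: 180·p(1−p)²(1−r)²
- 2018-2019 only: 180·p(1−p)(1−r)[1−p(1−r)]

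At p = 0.3, r = 0: 26.5 + 26.5 = 52.9 (from unrounded values). At p = 0.3, r = 0.7: 2.4 + 10.3 = 12.7. These are the extremes over the grid. With r from 0.3 to 0.7 the range is 12.7 to 34.5.

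**2. Strata in the linear models.** The documents' only power figure for antibody response is SAP Table 8, the pairwise difference in proportions with 27 per arm. An exact likelihood-ratio calculation gives power of 0.79 to 0.82 at its five rows, so it reproduces. It says nothing about the log-titer models, and no stratum effect is given anywhere. Assume the strata explain R² of the variance.

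Planned over adjusted standard error is approximately 1/√(1−R²), less a small cost in degrees of freedom: 1/√0.95 = 1.026, 1/√0.90 = 1.054, 1/√0.80 = 1.118.

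Simulation used 162 evaluable subjects (27 × 6), five unequal sites, two vaccine strata, permuted blocks of 6 (assumed), both planned interactions, and 10% of 4-month-arm subjects vaccinated between doses (assumed). Planned/adjusted standard error ratios:

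| Model, prognostic factor | R² = 0 | 5% | 10% | 20% |
|---|---|---|---|---|
| 2A, site | 0.997 | 1.023 | 1.053 | 1.118 |
| 2A, vaccine stratum | 0.997 | 1.024 | 1.052 | 1.118 |
| 2B, site | 0.995 | 1.020 | 1.050 | 1.115 |
| 2B, vaccine stratum | 0.995 | 1.003 | 1.013 | 1.036 |

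A separate simulation of 2A shows where the excess lies. At R² = 20% the empirical SD of the estimate was 0.2505 unadjusted and 0.2449 adjusted, while the mean reported standard error was 0.2737 and 0.2450. Test size at a nominal 5% was 3.6% unadjusted and 5.3% adjusted.

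Model 2A has 6 parameters, so 162 − 6 = 156 residual degrees of freedom. Five sites and one vaccine indicator use 4 + 1 = 5 of them.

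**3. Why not the vaccine stratum in 2B.** The two vaccine-history terms of 8.3.2 already carry 44-83% of the stratum's variance over the grid above. Adding the stratum inflates the standard error of each history term by √[(1−R²ₓ)/(1−R²ₓ₊ₛ)]. Here R²ₓ is that term's squared correlation with the other history term, and R²ₓ₊ₛ is the same with the stratum added. At p = 0.5, r = 0 the factors are 1.095 (prior seasons) and 1.265 (2018-2019). At p = 0.3, r = 0.7 they are 1.217 and 1.611. The inflation is therefore 10-22% and 26-61%, against a gain in the treatment terms of 0.3, 1.3 or 3.6%.

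**The case against.** **On the seasons.** A reader might infer that 6.4 simply governs the model covariates. The documents do not support that: 6.4 defers to Section 8.3, 8.3.2 lists the right seasons, and the faulty pair sits in a sentence about summaries. The Table 56, 68 and 76 shells carry the right row labels, and the neighbouring tables follow those formats. A programmer would have to override both to miscode anyone, so the recoding count is a worst case. The 8.3.1 wording is loose rather than a rival definition. All of this stands. It does not remove the conflict, because the matrix definition still points to 6.4.

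**On the strata.** SAP 6.7 omits site openly and with a reason, and no figure in the documents shows a centre effect. If there is none, adjustment costs a little. Model 2A is also the deliberately unadjusted member of a pair. These points stand, and they are why this is offered as an improvement with the unadjusted 2A retained. The 6.7 reason concerns procedures and the laboratory. It does not address differences between site populations, and it gives no reason for leaving out the vaccine stratum.

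**On putting both strata everywhere.** This is tempting, but the effect of prior seasonal vaccination is itself an exploratory objective (protocol 3.1.3, SAP 3.1.3), and in 2B the stratum would damage the terms that estimate it. In the logistic models, adjustment changes the odds ratio being estimated.

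**Conclusion.** The season pair in SAP 6.4 is wrong as written and should be corrected before programming. If it were followed, 13 to 53 of 180 subjects would be recoded under the assumed uptake and correlation, and only exploratory outputs would change.

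Using the strata in the linear models is a worthwhile, low-cost gain for both factors in 2A and for site in 2B. Its size rests entirely on an assumed R²: a cost of 0.3-0.5% in standard error at zero, and otherwise the planned standard errors are about 2, 5 or 12% too wide at 5, 10 or 20%. A reader might infer that leaving the strata out invalidates the tests. It does not: the error is on the conservative side. The primary by-arm summaries use no model and are unaffected, and the logistic models need no strata.

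**What to change.** 1. In SAP 6.4, replace 2018-2019 with 2017-2018 in the prior-season pair and keep 2018-2019 as a separate term. The back-reference in 8.3.2 is then harmless.
2. Reword SAP 8.3.1 to state the Table 56 cross-classification: 2016-2017 and/or 2017-2018, crossed with 2018-2019.
3. In SAP 8.3.2, add site and the vaccine stratum, both as recorded at randomisation, to Model 2A. Keep the fully unadjusted 2A as a sensitivity analysis.
4. Add site only to Model 2B. Leave the vaccine stratum out of 2B, and leave the logistic models without strata.
5. Amend SAP 6.7 to match.

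Cost: two wording corrections, the 2A and 2B equations with their covariate text, one sentence in 6.7, footnotes on Tables 72-79, and a repeat of Tables 72-75 for the unadjusted version. Both variables are already in the randomisation file. The price is 5 degrees of freedom in 2A and 4 in 2B with five sites, or one more in each if the sixth site column in the shells of Tables 19 and 20 is used.

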6.5. Missing Data

All attempts will be made to collect all data per protocol. As missing data are expected to be minimal, no imputation will be performed for missing values. Any data point that appears to be erroneous or inexplicable based on clinical judgment will be investigated as a possible outlier. If data points are identified as outliers, sensitivity analyses will be performed to examine the impact of including or excluding the outliers. Any substantive differences in these analyses will be reported.

6.6. Interim Analyses and Data Monitoring

Interim analyses will only be used to terminate this trial in the event that unanticipated safety events deemed to be of sufficient concern require such action by the sponsor. These assessments will not be made on the basis of testing a formal statistical hypothesis; therefore, p-value adjustment will not be made to any analyses. A DSMB will be convened by DMID to review study progress and participant, clinical, safety, and reactogenicity and immunogenicity data.

Emergent public health needs may dictate additional interim safety, reactogenicity, and/or immunogenicity analyses be performed on available information at any time during the trial. If this occurs, immunogenicity data will be analyzed as results are available from the central immunogenicity laboratory.

6.6.1. Interim Safety Review

An interim safety review may include enrollment and demographic information, medical history, concomitant medications, physical assessments, clinical laboratory values, dosing compliance, and solicited and unsolicited AE/SAEs. Additional data may be requested by the DSMB, and interim statistical reports may be generated as deemed necessary and appropriate by DMID. The DSMB may receive data in aggregate and presented by study group. The DSMB may also be provided with expected and observed rates of the expected AEs in an unblinded fashion and may request the treatment assignment be unblinded for an individual subject if required for safety assessment. The DSMB will review grouped and unblinded data in the closed session

only. The DSMB will meet and review this data at trial-specific time frames or ad hoc as needed during this trial as defined in the DSMB charter. As an outcome of each review/meeting, the DSMB will make a recommendation as to the advisability of proceeding with study vaccinations, as applicable, and to continue, modify or terminate this trial.

The interim safety reports generated for the DSMB are not intended to be published; they will be used only for informing emergency preparedness.

Additionally, this trial will be monitored to determine if any of the halting rules described in Protocol Section 9.5 are met.

